## **2.1. Immunotherapy Response Assessment in Neuro-Oncology (iRANO)**

Previous assessment criteria were done for cytotoxic chemotherapy where the response if it occurs does so within a few weeks of treatment onset and can be measured by tumor shrinkage. Recent studies with immunotherapeutic agents such ipilimumab have shown 4 types of responses: a rapid tumor shrinkage, a prolonged stable disease followed by a slow reduction in tumor burden, an initial increase in tumor size followed by a later sustained shrinkage of the tumor and a shrinkage of the tumor despite the appearance of new lesions. The response also tended to be relatively delayed and may not occur until the post-induction period of therapy. Using the immune-related response criteria (irRC) the ipilimumab melanoma trial would have identified 10% more patients as responders (36).

The Response Assessment for Neuro-Oncology (RANO) criteria were initially proposed in 2010 to improve radiologic assessment of GBM and to encompass pseudo progression and pseudo response phenomenon. A revision for immunotherapy was published in November 2015 (37). It incorporates the irRC and the RANO criteria. The new criteria addresses the issue of initial progressive imaging findings in the context of

patients with neuro-oncological malignancies with a goal of decreasing the likelihood of premature discontinuation of potentially beneficial therapies while ensuring maximum patient safety. The iRANO institutes a 6 months mark whereby radiographic deterioration or new lesions do not constitute progression unless confirmed with a second MRI or CT scan done at least 3 months later. Clinical neurological decline irrespective of imaging findings constitute progression provided the decline cannot be explained by comorbidities or a change in the corticosteroid dose. Radiographic evidence of progression noted after 6 months of instituting immunotherapy is considered tumor progression and do not require confirmation (37) (see section iRANO and appendix 1 for algorithm).

Patients, because the actual duration of pseudoprogression and the time for immunotherapies to become effective are still unknowns will be allowed at the investigator and patient discretion to continue on study treatment during the 3 month period and even after there is confirmation of radiographic or clinical progression unless there is significant drug toxicity.

## **2.2. Immunoscore**

It has become accepted that the host immune contexture has significant value in tumor prognostication and grade. The Immunoscore quantifies two lymphocytes population: CD3/CD45RO and CD3/CD8 within the tumor core and the invasive margin and assigns a score of 0 to 4 with the latter indicative of high density of immune infiltration. This score has been shown in two cohorts of colorectal cancer patients (n=602) to be highly predictive of tumor recurrence and survival at 5 years (38).

In this study using an anti-PD-L1 in patients with GBM the predictive power of the Immunoscore and thus its potential future use as a biomarker in this cancer population will be explored.

## **3. OBJECTIVES OF THE STUDY**

### **3.1. Primary Objective**

To determine the safety and tolerability of avelumab 10mg/kg administered IV Q2weeks in patients receiving standard therapy for newly diagnosed GBM.

### **3.2. Secondary objectives**

To determine the impact of the addition of avelumab in patients receiving standard therapy for newly diagnosed GBM on overall survival, progression free survival and other antitumor activity parameters according to the immunotherapy Response Assessment for Neuro-Oncology (iRANO) at 52 weeks and every 52 weeks thereafter.

### **3.3. Exploratory objectives**

To explore biomarkers that could predict treatment response to avelumab such as: the tumor immunoscore, presence and extent of PD-L1 expression on tumor cells and microglia/macrophages within the tumor

To correlate the OS and PFS to the baseline value and the change from baseline to week 52 and every 52 weeks /or the end of study neurocognitive function as measured by the evoked potential P300 (normal), the baseline corticosteroid dose, the total cumulative corticosteroid dose over the whole study duration, the total cumulative dose of temozolomide since diagnosis and the incidence and severity of irAE's.

To assess and compare above mentioned biomarkers in tissue samples from patients with second surgical resection i.e. treatment failures

To estimate in this GBM population the duration of pseudoprogression and the lagtime needed for immunotherapy to become effective.

## **4. STUDY DESIGN**

### **4.1. Overview of Study Design**

This is a single center, phase 2, open label, open-ended, add-on, single dose study of maximum duration of 260 weeks in patients receiving standard therapy for newly diagnosed GBM. In total 30 patients who meet the entry criteria will be entered into the study within 3 weeks of finishing their last day of combined radiotherapy/temozolomide. Avelumab will be initiated concurrently with the initiation of the first 5 days, monthly cycle of temozolomide.

The study will consist of 3 different phases: Combination Phase a Monotherapy Phase and an Extended Safety Follow-up Phase.

### **4.2. Treatment Phases of the Study**

**Combination Phase:** Upon completion of the standard combination therapy of radiotherapy (total dose 60 Gy, administered as daily 2Gy fractions, 5 days/week or as per local standard) and temozolomide (75 mg/m^2/day p.o. qd) and a treatment break of no more than 21 days, the combination phase will start. Patients will receive temozolomide and avelumab for 6 cycles of 28 days each. During the 1st cycle Temozolomide will be given the first 5 days at a dose of 150mg/m^2/day p.o. In the next cycle, the temozolomide dose should be escalated to 200/mg/m^2 if permitted by the patient's hematological and non-hematological toxicity profile (as per NCI-CTC AE version 5). The temozolomide dose will be adjusted according to hematological and non-hematological toxicity as per temozolomide's product monograph (appendix 4). Avelumab will be administered on day 1 and day 15 of each cycle at a dose of 10mg/kg IV. Avelumab therapy will be withheld according to the occurrence and severity of avelumab emergent adverse events as per table 3. Patients will continue the

combination of temozolomide (150 – 200mg/m^2 per day PO X5 days Q28days) and avelumab (at 10mg/kg dose, IV on days 1 and 15 per cycle) until 6 cycles are completed or until the occurrence of a termination event.

**Monotherapy Phase:** Upon completion of the Combination Phase or upon stopping temozolomide because of temozolomide related toxicity/tolerability issues or patient choice, the patient will continue into the avelumab Monotherapy Phase. Avelumab 10mg/kg IV Q2weeks will be continued as monotherapy until the occurrence of a termination event defined as one of the following: 1) clinical evidence of neurological deterioration resulting in an ECOG score of at least 3 or more, unexplained by other comorbidities, unchanged by an increase in corticosteroid dose and sustained for at least two weeks or 2) treatment emergent adverse event (TEAE) of grade 3 or more or 3) withdrawal of patient consent.

Patients who experience irAE's may according to table 3 directives have their avelumab therapy suspended.

The use of Bevacizumab or re-irradiation will not be allowed in the study and will be considered as evidence of a termination event.

Patients will be promptly informed upon confirmation of disease progression as per the new iRANO criteria. They will be offered to pursue with the avelumab therapy as monotherapy or in combination with other therapies or to withdraw from therapy and enter the Extended Safety Follow up phase. They will need to be reconsented before allowed to continue with the avelumab therapy.

#### **Extended Safety Follow-up Phase:**

Patients who discontinue avelumab therapy for any reason at any point in the study will be entered into an extended safety follow-up period of 90 days. New treatment will then be at the investigator or local oncologist's suggestion. All subjects will be observed for the possible occurrence of delayed irAE's for survival data and information about subsequent therapies will be collected. Tissue samples in patients undergoing second surgical resections will be obtained for further biomarker analysis.

#### **4.3. Treatment Allocation**

This is an open label, open- ended, single center add-on study

#### **4.4. Number of Subjects**

A total of 30 patients will be recruited.

## **4.5. Centers**

This is a single center investigator initiated study.

## **5. ENDPOINTS**

### **5.1. Primary**

Safety and tolerability based on avelumab treatment emergent adverse events leading to permanent or transient discontinuation of avelumab

Treatment emergent adverse events of special interest will include those of autoimmune origin (irAE).

The adverse events will be graded according to the National Cancer Institute Common Terminology Criteria for Adverse Events, version 5.0

### **5.2. Secondary**

Radiological tumor response will be graded according to the Immunotherapy Response Assessment for Neuro-Oncology (iRANO) criteria by a single study radiologist based on the gadolinium enhanced brain MRI or CT scan performed at the study center at baseline and Q52weeks or within 2 weeks of an end of study visit and evaluations of locally obtained MRI's or CT scan.

Clinical tumor response as per the iRANO criteria will be evaluated by the principal investigator based on the protocol specified neurological exams

The iRANO endpoints will be stratified in relation to MGMT status, baseline age (>50yrs), baseline Karnofsky performance score (score of 100), radical tumor resection vs biopsy, primary versus secondary GBM.

Changes in the daily corticosteroid dose will be discouraged during the 2 weeks period prior to the week 52 or end of study visit MRI or CT scan.

### **iRANO:**

#### ***During the study***

#### **Progression of Disease (PD) based on clinical parameters:**

Patients at any time with significant, clinical neurological deterioration resulting in an ECOG score of 3 or more, sustained for more than 2 weeks, unchanged by an increase in steroids or unexplained by concurrent comorbidity will be considered as having progressed and confirmatory imaging will not be required.

The SPD is the sum of the products of biperpendicular diameters of the measurable enhancing lesions (max 5 lesions).

**Progression of Disease (PD) based on radiographic parameters:**

Patients with stable clinical neurological status with stable dexamethasone dose of 12mg/day or less and evidence of radiological progression defined as a  $\geq 25\%$  increase in the sum of the biperpendicular diameters of enhancing disease; or substantial worsened T2/FLAIR; or new lesions on gadolinium enhanced MRI or CT scan done less than 6 months from baseline will require confirmation on a repeat imaging done 3 months later. The first MRI or CT scan showing progression will act as the new baseline and if progression is confirmed the date of progression will be backdated to the new baseline MRI or CT scan where the progression was first noted.

If the first radiological evidence of progression or new lesions occurs 6 months or more from baseline then no confirmatory imaging will be required.

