***At week 260 or end of study visit***

**Progression of Disease (PD)** will be defined as a  $\geq 25\%$  increase on the 12 month MRI in the sum of the product of the biperpendicular diameters of enhancing disease; or new lesions; or substantial worsened T2/FLAIR; or significant clinical neurological decline unexplained by a change in medication or concurrent comorbidities. The SPD is the sum of the products of biperpendicular diameters of the measurable enhancing lesions (max 5 lesions)

**Complete Response (CR)** will be defined as the disappearance on the month 12 MRI or CT scan of all enhancing disease, no new lesions, with stable or improved T2/FLAIR; no more than physiological steroids; clinically stable or improved

**Partial Response (PR)** will be defined as a  $\geq 50\%$  decrease on the month 12 MRI or CT scan in the sum of the products of the biperpendicular diameters of enhancing disease, no new lesions, stable or improved T2/FLAIR, stable ( $>2$  months) or decreased steroid dose, clinically stable or improved

**Stable Disease (SD)** will be defined as a patient who do not qualify for complete response, partial response, or progressive disease, stable or improved T2/FLAIR; stable ( $>2$  months) or decreased steroid dose, clinically stable or improved

**Overall survival (OS)** will be defined as the time from baseline to the date of death from any cause. Follow up times of patients who are lost to follow up will be recorded and censored. The censoring time point (date last known to be alive) will be recorded.

**Objective Response Rate (ORR)** will be defined as the number of patients with CR + PR - divided by the total number of patients at time points 12, and every 12 months thereafter.

**Progression Free Survival (PFS)** will be defined as the time from baseline to documented PD or death from any cause. Patients without event would be censored at the last valid tumor assessment (before starting new anti-cancer therapy) at which they were known to be progression-free.

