For index lesions the Sum of the Product of the biperpendicular Diameters of the measurable enhancing lesions (SPD) will be recorded and used for comparison. An increase in the lesion SPD noted prior to month 6 will require confirmation 3 months later using the last MRI or CT scan as baseline comparison. The 12 months MRI or CT scan will be compared to baseline.

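### Protocol 5.2 measures early radiographic progression by the sum of diameters, while the 12-month definition and the SAP use the sum of products

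*Protocol*

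**What the plan says.** Four places bear on how tumour size defines progression.

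- **Protocol 5.2, radiographic progression during the study.** The size criterion is a 25% or greater "increase in the sum of the biperpendicular diameters of enhancing disease". It stands in a sentence about scans under 6 months from baseline, which need a repeat scan 3 months later. For later scans the section changes only the confirmation rule: "If the first radiological evidence of progression or new lesions occurs 6 months or more from baseline then no confirmatory imaging will be required". It gives them no size measure of their own.
- **Protocol 5.2, week 260 or end of study visit; Protocol 12.3.2; SAP 1.3.2.** The same 25% is applied to the 12-month scan, but measured "in the sum of the product of the biperpendicular diameters of enhancing disease".
- **Protocol 5.2, clinical progression, directly before the radiographic rule.** The measure is defined here: "The SPD is the sum of the products of biperpendicular diameters of the measurable enhancing lesions", up to five lesions.
- **Protocol 9.3.5.** SPD is the quantity to be recorded and compared for index lesions. "An increase in the lesion SPD noted prior to month 6 will require confirmation 3 months later". No percentage is attached. The 12-month scan is compared with baseline.

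The SAP gives only the 12-month definition and has no rule for earlier scans.

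**The concern.** A sum of diameters is a length and a sum of products is an area, so 25% of one is not 25% of the other. A reader who applies the radiographic rule in Protocol 5.2 as worded, and one who applies SPD as Protocol 9.3.5 suggests, can classify the same early scan differently.

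What depends on the choice:

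- **PFS event dates.** Under Protocol 5.2 a confirmed early progression is backdated to the scan that first showed it, so the trigger fixes the date on the Kaplan-Meier curve.
- **Pseudoprogression.** Protocol 5.3 describes how long radiological progression was seen in clinically stable patients before it stabilised or regressed. That period starts at the same trigger.
- **The one-year PFS criterion.** Protocol 12.3.2 and SAP 1.3.2 conclude benefit if 11 or more of 30 patients are alive and progression-free. With so small a count, one reclassified patient could matter.
- **Consequences for patients.** Progression by iRANO also bears on informing and re-consenting patients (Protocol 4.2), discontinuation (6.2) and the end of treatment visit (9.3.4).

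**Working it through.** The plan gives no area-growth figure to reproduce. The only input from the documents is the 25% threshold. All lesion shapes and sizes below are assumptions for illustration.

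**1. Both diameters grow equally.** If every diameter is multiplied by k, the sum of diameters grows by k and SPD by k².
- Diameters +25%: 1.25² = 1.5625, so SPD +56.25%.
- SPD +25%: √1.25 = 1.118, so diameters +11.8%.

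In this case, growth of 25% to 56% in area is progression under the SPD rule but not under the diameter rule.

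**2. One lesion, only one diameter grows.** Let the growing diameter be a and the other b. A 25% rise in a + b adds 0.25(a + b) to a, so the area grows by 0.25(1 + b/a).

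| Long:short axis | Long axis grows | Short axis grows |
|---|---|---|
| 1:1 | 50% | 50% |
| 2:1 | 37.5% | 75% |
| 3:1 | 33% | 100% |

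Since b/a is positive, the result always exceeds 25%.

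**3. Two round lesions of 30 and 10 units, only one grows.** The sum of diameters is 2(30 + 10) = 80, and 25% of it is 20, or 10 on each diameter of the growing lesion. Baseline SPD is 900 + 100 = 1000.
- Larger grows to 40: 1600 + 100 = 1700, SPD +70%.
- Smaller grows to 20: 900 + 400 = 1300, SPD +30%.

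**4. A case in the other direction.** Take one 30 × 30 lesion and four 5 × 5 lesions, with only the small ones growing. The sum of diameters is 60 + 40 = 100. The added 25 is shared over eight small diameters, 25/8 = 3.125 each, giving 8.125. SPD goes from 900 + 4 × 25 = 1000 to 900 + 4 × 8.125² = 1164, or +16%. Here the diameter rule is met before the SPD rule.

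**5. Which scans are affected.** The size sentence expressly covers scans under 6 months. For months 6 to 12, Protocol 9.3.5 sends local scans, usually taken every 3 to 4 months, to the iRANO criteria on page 29, where the contents list places section 5.2. No other size threshold is given for that period, so the diameter wording carries over by inference only.

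**6. The one-year count.** Take a tumour past 25% but under 56% in area on an early scan, with equal growth.
- If it is still at least 25% above baseline at month 12, the SPD rule makes it progression on that scan. Assuming a call on that scan counts against the one-year number, the patient is not progression-free under either wording, and only the date differs.
- If it has fallen back below 25%, or the month-12 scan is missing, the two wordings can give different one-year results. Even then, a scan under 6 months needs confirmation before it counts.

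For scale, with the plan's 27% under no effect and n = 30, the exact binomial probability is 0.16 for 11 or more and 0.28 for 10 or more. These lie on either side of the plan's 0.2 level, so one patient can decide the result. How many patients would be reclassified cannot be computed from the documents.

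**The case against.** The strongest reply is that the early rule has only lost the reference to a product. SPD is defined immediately before it, under the same during-the-study heading, where the clinical criterion has no use for it. Protocol 9.3.5 says SPD is what is recorded and compared, including before month 6, and nothing in the plan has a sum of diameters recorded. A slip is therefore plausible. That weakens any claim about what readers will do, but it does not remove the conflict. The radiographic sentence does not refer to SPD, and Protocol 9.3.5 supplies no percentage. The 25% can be read in from the reference to iRANO, but the one explicit early threshold is worded in diameters.

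A reader might infer more than the documents support:

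- **That every scan before month 12 requires 56% area growth.** This needs the literal wording, equal growth in both diameters, and extension of a sentence about scans under 6 months to months 6 to 12.
- **That progression takes twice as long to reach, or slips by a scan.** The factor of two assumes exponential growth in area, which the documents do not state. New lesions, worsened T2/FLAIR and clinical decline are also separate routes to progression.
- **That one-year PFS is biased upward.** The month-12 SPD scan would catch most late calls. Later dating is the usual direction, but step 4 shows it is not certain.
- **That Protocol 9.3.5 sets a separate trigger at any SPD increase.** The sentence says when confirmation is needed, and the 25% may be intended.

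It is also fair to say that PFS is a secondary endpoint in a 30-patient single-arm study whose primary endpoint is safety.

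**Conclusion.** The radiographic progression definition is internally inconsistent and should be fixed. Protocol 5.2 uses the sum of diameters for early scans, expressly under 6 months and by inference to month 12. The 12-month definition, Protocol 12.3.2 and SAP 1.3.2 use SPD at the same 25%, and Protocol 9.3.5 uses SPD without a percentage.

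On the literal wording the early threshold is about 56% in area for equal growth, about 30% to 100% in the other shapes tried, and 16% in the example with several small lesions. Size-based progression would therefore usually be dated later on early scans than under the SPD rule. The exposure is mainly to PFS event dates and the pseudoprogression description. An effect on the one-year count is possible only in the circumstances in step 6 and is not shown. This rests on the assumed lesion geometry and on the literal reading. If product was meant throughout, the remedy is a correction of wording.

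**What to change.** For endpoint assessment, state one measure and one threshold for every scan: a 25% or greater increase in SPD. The Protocol already defines and records this measure and the SAP already uses it.

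- **Protocol 5.2, radiographic progression:** replace the sum of diameters with SPD, and say expressly that the measure also applies to scans from month 6 to 12.
- **Protocol 9.3.5:** attach the 25% to the SPD increase that needs confirmation before month 6.
- **Protocol 12.3.2 and SAP 1.3.2:** use the same sentence, and add the early-scan rule, with its confirmation and backdating, to the SAP.

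Because iRANO progression also bears on re-consent, discontinuation and the end of treatment visit, the sponsor should confirm that the reconciled wording is what is intended in Protocol 4.2, 6.2 and 9.3.4.

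The cost is wording only. The downside is that PFS may look slightly shorter than under the diameter wording.

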***At week 260 or end of study visit***

**Progression of Disease (PD)** will be defined as a  $\geq 25\%$  increase on the 12 month MRI in the sum of the product of the biperpendicular diameters of enhancing disease; or new lesions; or substantial worsened T2/FLAIR; or significant clinical neurological decline unexplained by a change in medication or concurrent comorbidities. The SPD is the sum of the products of biperpendicular diameters of the measurable enhancing lesions (max 5 lesions)

**Complete Response (CR)** will be defined as the disappearance on the month 12 MRI or CT scan of all enhancing disease, no new lesions, with stable or improved T2/FLAIR; no more than physiological steroids; clinically stable or improved

**Partial Response (PR)** will be defined as a  $\geq 50\%$  decrease on the month 12 MRI or CT scan in the sum of the products of the biperpendicular diameters of enhancing disease, no new lesions, stable or improved T2/FLAIR, stable ( $>2$  months) or decreased steroid dose, clinically stable or improved

**Stable Disease (SD)** will be defined as a patient who do not qualify for complete response, partial response, or progressive disease, stable or improved T2/FLAIR; stable ( $>2$  months) or decreased steroid dose, clinically stable or improved

**Overall survival (OS)** will be defined as the time from baseline to the date of death from any cause. Follow up times of patients who are lost to follow up will be recorded and censored. The censoring time point (date last known to be alive) will be recorded.

**Objective Response Rate (ORR)** will be defined as the number of patients with CR + PR - divided by the total number of patients at time points 12, and every 12 months thereafter.

**Progression Free Survival (PFS)** will be defined as the time from baseline to documented PD or death from any cause. Patients without event would be censored at the last valid tumor assessment (before starting new anti-cancer therapy) at which they were known to be progression-free.

